Results of statistical models (ie, least-squares means, confidence intervals, risk differences) will be rounded to one additional decimal place from the original data, or a maximum of two decimal places. Standard error will be reported to an additional level of precision. Results which cannot be determined will be displayed as "NA", "NE", or similar.

For tests of hypothesis of treatment group differences, the associated p-value will be reported. All p-values will be rounded to four decimal places after assignment of statistical significance; pvalues that round to 0.0000 or are reported by SAS as zero will be presented as "≤0.0001"; pvalues that round to 1 or are reported by SAS as 1 will be presented as ">0.9999". P-values which are significant at a 0.05, 0.025, 0.01, 0.001, or 0.0001 level will be marked with asterisks. P-values which cannot be determined will be displayed as "NA". P-values are descriptive for outcomes and analyses not included in the multiplicity algorithm.

Date of last dose is collected on the *Treatment Discontinuation/Completion* eCRF page. For patients with missing or partial date of last dose, the date of last dose (ie, treatment end date) will be imputed. Date of last dose will be imputed as follows:

- Derive the number of tablets taken at the last visit as the dispensed amount minus the returned amount. For treatment compliance (Section 7.3) and exposure (Section 9.2), if the returned amount is missing, it will be assumed that zero tablets were taken. Otherwise, it will be assumed that 60 tables were taken.
- An estimated date of possible last dose will be calculated by adding the number of tablets taken divided by 2 to the visit date associated with the last visit where drug accountability was collected.
- If there is a partial date of last dose, missing day will be imputed using the day from treatment start date, or the last day of the month if that month has fewer days than the treatment start month.
- Treatment end date will be the minimum of the partial date of last dose, calculated estimated date of possible last dose, and collected study discontinuation/completion date.

Summary tables and data listings:

- Unless otherwise specified, no preliminary rounding will be performed; rounding will only occur after analysis.
- Data from patients excluded from an analysis population will be presented in the data listings but will not be included in the calculation of summary statistics, where applicable.

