# 7.3. Measures of Treatment Compliance

Patients will strive for 100% compliance with the daily dosing schedule. Treatment compliance will be summarized as percent of planned dose received for each dosing regimen. Percent of planned dose received will be calculated for the entire treatment period as follows:

100\*(Tablets Dispensed-Tablets Returned)/(Tablets Expected)

Tablets Expected is defined as the time on treatment multiplied by the expected number of pills taken daily (x2 for the 12 mg BID group; x2 for the 8 mg BID group; x2 for the placebo group), where time on treatment is defined as treatment end date – treatment start date + 1. Dose

interruptions will be ignored in this calculation. Derived patient compliance, compliance per the eCRF (80% or higher versus less than 80%), and dosing exceptions will be listed in by-patient data listings.

For patients who roll over into one of the open label extension studies, it will be assumed that only 1 dose of study drug was administered for the last dose of study drug. For patients who do not roll over, it will be assumed that 2 doses of study drug were administered for the last dose of study drug.

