#### 9.5. Clinical Laboratory Evaluation

Clinical laboratory samples should be collected at the beginning of each clinic visit and just prior to a dose on all Study Visit Days and will be processed by a central laboratory. In the event a patient is unable to attend an in-clinic visit due to COVID-19, clinical laboratory blood draws may be performed by a Home Health Care agency or a local laboratory.

Clinical laboratory variables will be presented in 4 ways. First, change from baseline to the minimum post-baseline value, maximum post-baseline value, and final value will be summarized. Baseline will be defined as the laboratory value obtained before the first dose of study drug on Day 1; if Day 1 values are unavailable, then values obtained at the Screening Visit will be used. Only post-baseline values on treatment will be eligible. The Follow-up Visit will be excluded from possible minimum, maximum, or final post-baseline values.

This analysis will be repeated with outlying values removed from eligibility for minimum and maximum values. An outlier is defined using the interquartile range (IQR). The IQR is equal to the third quartile minus the first quartile and will be calculated by visit and treatment group for each numeric parameter. The IQR will be multiplied by a constant of 1.5. Any value which is above 1.5 times IQR plus the third quartile or below 1.5 times IQR minus the first quartile will be considered an outlier and will be removed from eligibility for minimum, maximum, or final post-baseline values.

Second, shift tables will summarize by treatment group and active overall the number and percentage of patients with categorical changes from baseline defined by the laboratory normal reference range for each laboratory parameter (Below reference range, Within reference range, and Above reference range). The baseline category will be cross-tabulated with post-baseline category ( $3 \times 3$  table). The post baseline category will be assigned and summarized in 2 ways for each laboratory parameter: minimum post-baseline value and maximum post-baseline value. Only post-baseline values on treatment will be eligible. Patients will only be reported in the shift tables if they have both a baseline and post-baseline value.

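### The SAP fills a missing day of last dose with the day of the month on which treatment started; the later minimum step keeps the early errors, so exposure is shortened and compliance inflated.

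*SAP*

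**What the plan says.** SAP section 4 (General Analysis and Reporting Conventions) sets the rule for a partial date of last dose: "If there is a partial date of last dose, missing day will be imputed using the day from treatment start date". One exception is allowed, and it turns on month length: "or the last day of the month if that month has fewer days than the treatment start month". The tablet-based candidate is formed by "adding the number of tablets taken divided by 2 to the visit date associated with the last visit where drug accountability was collected". The last step is: "Treatment end date will be the minimum of the partial date of last dose, calculated estimated date of possible last dose", with the recorded study discontinuation/completion date as the third candidate.

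The end date is used in these places:

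- **SAP 7.3, compliance.** It is 100 × ("Tablets Dispensed-Tablets Returned)/(Tablets Expected"). Tablets expected are two per day of treatment, and "time on treatment is defined as treatment end date" minus start date plus 1.
- **SAP 9.2, exposure.** The same span gives days in the study. Days dosed are that span minus days with dosing exceptions.
- **SAP 6.1 and 8.5, Kaplan-Meier displays.** These are time to early treatment termination, and time to first SALT ≤20, where non-responders are censored at treatment end.
- **SAP 9.5, laboratory summaries.** "Only post-baseline values on treatment will be eligible", with no definition of on-treatment by date.

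No section makes an exception for a stop in the month of starting.

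**The concern.** The start day is fixed at randomisation and says nothing about the stop day, so the imputed date is arbitrary within the recorded month. Taking a minimum afterwards makes the error one-sided. It can remove an imputed date that is too late, but never one that is too early. What survives is understated exposure and overstated compliance.

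The same-month stop is the clearest failure, because the imputed date is the start date itself. One such patient could put an impossible maximum into the compliance table and a false one-day exposure into the safety report.

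The month-length exception is also keyed to the wrong condition. It asks whether the stop month is shorter than the start month, not whether the start day exists in the stop month.

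**Working it through.** The documents give no figure on this point, so there is none to reproduce. The SAP rules were applied directly to calendar dates.

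**Formulas.** Candidate date = start day placed in the recorded month, or the last day of that month if it is shorter than the start month. End = earliest of the candidate, the tablet estimate and the study end date. Days = end − start + 1. Compliance = 100 × tablets taken / (2 × days).

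**1. Stop in the start month.** A month is not shorter than itself, so the exception cannot apply and the candidate is the start date. The other two candidates cannot precede Day 1. So end = Day 1, days = 1, tablets expected = 2, and compliance = 100 × T/2 = 50% × T.

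| Tablets counted as taken | Fully dosed days | Days under SAP | Compliance |
|---|---|---|---|
| 6 | 3 | 1 | 300% |
| 14 | 7 | 1 | 700% |
| 20 | 10 | 1 | 1000% |
| 22 | 11 | 1 | 1100% |
| 44 | 22 | 1 | 2200% |
| 60 (one bottle, Protocol 9.4.2) | – | 1 | 3000% |

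The 44-tablet row is a 3 May start with a 24 May last dose; the true values are 22 days and 100%. Compliance passes 1000% only when T > 20, that is, 11 or more fully dosed days. In a 31-day month there are 31 × 32/2 = 496 possible start/stop pairs, of which 21 × 22/2 = 231 (47%) span at least 11 days. If the returned amount is missing, section 4 counts zero tablets and compliance is 0%. Days dosed (SAP 9.2) can fall below 1 once dosing exceptions are subtracted.

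**2. Later stops, single cases.**
- Start 1 May, last dose 31 July: candidate 1 July, 30 days early.
- Start 10 May, last dose 24 October (Day 168): candidate 10 October. That gives 154 days instead of 168, and compliance of 100 × 336/308 = 109%.
- Start 20 May, last dose 3 November (Day 168): candidate 30 November. A study end date of 4 November pulls it back to 1 day late.

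**3. Later stops, overall.** Assumptions: starts spread evenly over 1 April to 31 December 2021 (275 dates); study end one day after last dose; tablet estimate no earlier than that. Every date was enumerated.
- *Last dose on Day 168:* after the minimum step, 83 start dates give an end 14 days early and 44 give one 16 days early. So 127/275 = 46.2% are at least 10 days early, and the other 148 are exact or 1 day late. Before the minimum step about 96% are at least 10 days off in one direction or the other.
- *Last dose evenly spread over Days 1 to 168:* 275 × 168 = 46,200 combinations. After the minimum step 8,543 (18.5%) are at least 10 days early. Before it about 52% are at least 10 days off.

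**4. Month-length exception.** A 3 May start with a June stop gives 30 June, because June is shorter than May. A 3 April start with a May stop gives 3 May. Day 3 exists in both stop months. With evenly spread stops, the start day exists in the recorded month in about 95% of uses of the exception.

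**The case against.** The best defence is that the imputed date is only one input to a minimum. The tablet estimate and study end date cap late errors, so the pre-minimum figures (96% and 52%) overstate the error in the date actually used. That stands, and only the post-minimum figures should be cited. The even spread of dates is also an assumption.

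Three stronger readings are tempting, but the documents do not support them:

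- **Any same-month stop gives compliance above 1000%.** It does not. That needs more than 20 tablets counted and a recorded return. With evenly spread stops, same-month stops are about 9% of cases, and those lasting 11 or more days about 4%.
- **Completers are always about two weeks off.** After the minimum step just over half are right to within a day. A completer also attends a dated Week 24 visit, and Protocol 9.4.3 has patients dose in clinic on visit days, so a missing day is unlikely there.
- **A patient dated to Day 1 loses all post-baseline laboratory values.** SAP 9.5 does not tie on-treatment to the imputed date, and its next sentence excludes by visit (the Follow-up Visit). A same-month stopper has at most two scheduled draws, Weeks 2 and 4. The laboratory effect is possible, not established.

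The month-length clause may have been meant to prevent non-existent dates, but it does not say so. A value such as 2200% would show in the by-patient listing, where derived and eCRF compliance both appear. That makes it detectable but does not correct the rule.

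**Conclusion.** The point holds as a minor one. Applied as written, the rule always gives Day 1 and a one-day duration when the day is missing and the recorded month is the start month. Nothing else in the SAP repairs that, and it rests on no assumption beyond the SAP text. For later stops the surviving error is early, by up to 30 days. The 46% and 18.5% figures depend on the stated spread of dates and on a study end date one day after the last dose. A later study end date would also leave some late errors.

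The effect is confined to patients with a partial last-dose date. The documents do not give their number, and it is probably small. Exposure, compliance and the two Kaplan-Meier displays are affected, and laboratory selection possibly. The primary endpoint does not use this date.

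**What to change.** In SAP section 4, replace the sentence so that a missing day becomes the last day of the recorded month, and delete the month-length exception. Keep the minimum with the tablet-based estimate and the study discontinuation/completion date. Add a floor: the result may not be earlier than the later of the first day of the recorded month and the treatment start date. This is close to the SAP's own rule for adverse-event end dates in section 9.3.

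In the 3 May example with a study end date of 25 May, the end date becomes 25 May: 23 days and 100 × 44/46 = 95.7%. With no usable study end date, suppose accountability is collected at Week 4 (31 May). The tablet estimate is then 31 May + 22 days = 22 June, so the end date is 31 May: 29 days and 100 × 44/58 = 75.9%. That is the downside: without a usable tablet estimate or study end date in the month, the date may be late by up to the rest of that month. The change does not alter the tablet estimate or the zero-tablet convention for a missing return.

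The cost is one SAP sentence and a few lines of derivation code, affecting only patients with a partial last-dose date.

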#### 5. ANALYSIS SAMPLES

The Efficacy Population will include all patients who are randomized in the study and dispensed study drug during the Treatment Period and were not treated at site 102. It was determined by the Sponsor during the course of the study that site 102 would be early terminated due to continued failure to comply with study procedures. The decision to exclude subjects treated at site 102 was made prior to unblinding.

The Modified Efficacy Population will include all patients who are randomized in the study and dispensed study drug during the Treatment Period. This population will include subjects from site 102 and will be used for sensitivity analyses of the primary and key secondary endpoints.

The Pharmacokinetic Population will include all patients who receive study drug and have at least 1 pharmacokinetic sample taken during the Treatment Period. Patients who receive placebo will be excluded from the Pharmacokinetic Population.

The Safety Population will include all patients who receive study drug during the Treatment Period. The Safety Population will include patients from site 102.

The Per Protocol Population will include all patients in the Efficacy Population who were dosed according to protocol and have no major protocol deviations. Further details on the identification of major protocol deviations are provided in Section 7.1.

In the event patients incorrectly receive treatment associated with a different treatment group, they will be analyzed "as randomized" for efficacy and "as treated" for safety if the patient received that treatment for more than 50% of doses.

## 6. STUDY SUBJECTS

#### 6.1. Disposition of Subjects

Disposition will be summarized by randomized treatment group and overall for all patients screened in the study. The following disposition information will be summarized (percentages based on the number randomized, with the exception of the reasons for discontinuation):

- The number of patients screened. Patients who rescreened will be counted only once.
- The number of patients randomized.
- The number and percentage of randomized patients within the Efficacy, Modified Efficacy, Pharmacokinetic, Safety, and Per Protocol Populations.
- The number and percentage of patients who completed treatment, defined as patients with either "Complete-Entering Open Label" or "Complete" noted for the question "Subject Status" on the *Treatment Discontinuation/Completion* electronic case report form (eCRF) page.
- The number and percentage of patients who completed treatment and enrolled in the Open Label Extension, defined as patients with "Complete-Entering Open Label" noted for the question "Subject Status" on the *Study Treatment Discontinuation/Completion* eCRF page.
- The number and percentage of patients who completed treatment and completed the follow-up visit (for those patients who did not enroll in the Open Label Extension), defined as patients with "Complete" noted for the question "Subject Status" on the *Treatment Discontinuation/Completion* eCRF page.
- The number and percentage of patients who prematurely discontinued treatment and the frequency and percentage of each discontinuation reason. The denominator for the percentage of each discontinuation reason will be the number of patients who discontinued treatment.
- The number and percentage of patients who prematurely discontinued treatment due to the COVID-19 pandemic and the frequency and percentage of each discontinuation reason. The denominator for percentage of patients who prematurely discontinued treatment due to COVID-19 will be the number of patients who discontinued treatment. The denominator for the percentage of each COVID-19 discontinuation reason will be the number of patients who discontinued treatment.
- The number and percentage of patients who completed the study, defined as patients with either "Complete-Entering Open Label" or "Complete" noted for the question "Subject Status" on the *Study Discontinuation/Completion* eCRF page.
- The number and percentage of patients who completed the study and enrolled in the Open Label Extension, defined as patients with "Complete-Entering Open Label" noted for the question "Subject Status" on the *Study Discontinuation/Completion* eCRF page.

- The number and percentage of patients who completed the study (for those patients who did not enroll in the Open Label Extension), defined as patients with "Complete" noted for the question "Subject Status" on the *Study Discontinuation/Completion* eCRF page.
- The number and percentage of patients who prematurely discontinued the study and the frequency and percentage of each discontinuation reason. The denominator for the percentage of each discontinuation reason will be the number of patients who discontinued the study.
- The number and percentage of patients who prematurely discontinued the study due to the COVID-19 pandemic and the frequency and percentage of each discontinuation reason. The denominator for percentage of patients who prematurely discontinued the study due to COVID-19 will be the number of patients who discontinued the study. The denominator for the percentage of each COVID-19 discontinuation reason will be the number of patients who discontinued the study due to the COVID-19 pandemic.

The number and percentage of patients randomized within each treatment group and overall will also be summarized by investigative site.

Disposition and patient visits will also be presented for each patient in patient data listings. Patient data listings will list date of informed consent, date of first/last treatment, date of end of treatment/early treatment termination, date of end of study/early study termination, and reasons for treatment or study discontinuation. A Kaplan Meier curve of time to early treatment termination for any reason will also be presented for the Safety Population. Patients who have completed treatment will be censored at date of last treatment, or 24 weeks. Screen failures will be provided in a separate listing. Rescreened patients who later enrolled will not be listed as screen failures.

#### 6.2. Demographic and Other Baseline Characteristics

Demographic characteristics (ie, sex, ethnic origin, race, age, and calculated body mass index) will be collected at the Screening Visit, between Day -28 and -1, and detailed on the eCRF. Demographic characteristics will be summarized using descriptive statistics for all randomized patients by treatment group and overall.

Baseline characteristics will be summarized using descriptive statistics for all randomized patients by treatment group and overall and will include the following:

- baseline total SALT score
- Alopecia areata classification (randomization strata via IWRS): partial scalp hair loss  $(SALT \ge 50 \text{ and } < 95)$ ; complete or near-complete scalp hair loss  $(SALT \ge 95)$
- duration of current episode in years (calculated as: [date of randomization date of current episode onset + 1] / 365.25)
- current nail involvement: yes; no (collected via eCOA system as 'HAND IMAGE CAPTURE')
- nasal hair involvement: yes; no (collected on the Physical Examinations eCRF page)
- eyebrow involvement: yes; no (collected as part of the BETA assessment)

- eyelash involvement: yes; no (collected as part of the BELA assessment)
- whether the patient has experienced any past and/or concomitant diseases, conditions, or exposures to serious infections such as HIV, or past surgeries: yes; no (collected via the Medical History Summary eCRF page)

Other co-morbidities may be identified and included as baseline characteristics.

All demographics and baseline characteristics will also be listed within a by-patient data listing for all randomized patients.

#### 6.3. **Prior and Concomitant Medications**

Concomitant medications will be recorded in the eCRF from Screening through study completion at Week 24 or the Follow-Up Visit at Week 28. All medications will be coded using the WHO Drug Dictionary Version 2020-SEP.

Medications are classified as prior if the medication started and stopped prior to the first dose date of study drug or as concomitant if used on or after the first dose date of study drug.

Prior and concomitant medications will be summarized with counts and percentages separately for the Safety Population by treatment group and overall, WHO Drug ATC classification level 2 and preferred term. For each summary, a subject will be counted only once for each medication.

Partial and completely missing dates will be imputed for the purposes of classifying concomitant medications as follows:

- Partial dates will be imputed following the same algorithm as in Section 9.3 for Treatment-emergent adverse events (TEAEs).
- For an entirely missing stop date (ie day, month, and year are missing), the medication will be treated as ongoing.

Prior and concomitant medications will also be listed by-patient.

#### 6.4. Medical History

Medical history will be coded with the MedDRA terminology Version 23.1 and summarized as counts and percentages for the Safety Population by treatment group and overall, system organ class, and preferred term. A patient will be counted only once for each condition. Conditions will be listed, including the verbatim investigator description of the relevant medical condition, the coded terms (system organ class, preferred term), start date, end date, and whether or not the condition is ongoing.

